4.3.4 Reasons for Withdrawal and Discontinuation of Vaccinations

Parents/guardians will be free to withdraw their child from the study at any time and for any reason, without penalty. Children who have received vaccine, regardless of the number of doses received, or who developed an AE or SAE will be strongly encouraged to remain in the study to be followed for safety purposes.

A child may withdraw or be withdrawn from the study for any of the following reasons:

- Withdrawal of consent of the parent or legal guardian.
- Withdrawal of assent of the child.
- As deemed necessary by the Principal Investigator or appropriate co-investigator for noncompliance or other reasons.
- Subject lost to follow-up.
- Early termination of the study.

The second or third study vaccination may not be administered to a child if any of the following criteria are met (although the child will remain in the study for safety follow-up visits):

- Medical condition for which continued participation, in the opinion of the Principal Investigator or appropriate co-investigator, would pose a risk to the child or would be likely to confound interpretation of the results.
- Presence of signs or symptoms that could confound or confuse assessment of study vaccine reactogenicity. For children with injection site or systemic signs or symptoms, or with an acute illness, including a tympanic temperature greater than 38.0°C, the study vaccination should/may be postponed/deferred until signs, symptoms, or acute illness have resolved and if within the acceptable protocol-specified window for that visit. If outside this window, the Sponsor must first approve the second or third study vaccination and the documentation of approval should be filed in the child's chart.

- Any unresolved or continuing solicited or unsolicited Grade 3 adverse event. An unresolved or continuing Grade 1 or Grade 2 adverse event is permissible unless, in the opinion of the Principal Investigator or appropriate co-investigator, it would render study vaccination unsafe or interfere with the evaluation of responses.

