- Grade 3 clinical safety laboratory value that does not decrease to Grade 2 or less prior to the second or third study vaccination. Any clinical safety laboratory parameter may be re-evaluated only once at the clinical laboratory prior to the second or third study vaccination. If the clinical safety laboratory value decreases to Grade 2 or less, the child may receive the second or third study vaccination. The second or third study vaccination should be scheduled to occur within the acceptable protocol-specified window for that visit. If outside this window, the Sponsor must first approve the study vaccination and the documentation of approval should be filed in the child's chart.
- Severe or sustained reaction or disability related to the first study vaccination.
- New onset of illness or condition that meets exclusion criteria.
- Child no longer meets eligibility criteria.
- As deemed necessary by the Principal Investigator or appropriate co-investigator for noncompliance or other reasons.
- Refusal of further study vaccination by the parent/guardian.
- Withdrawal of consent of the parent or legal guardian.
- Child lost to follow-up.
- Early termination of the study.
- New information becomes available that makes further vaccinations unsafe.

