4.3.6 Termination of Study

If a dose of vaccine is considered significantly reactogenic (see Section 8.5) dose escalation and/or additional vaccinations will be suspended until reviewed by the Independent Medical Monitor, SMC, and study sponsor. Any recommendation of the Independent Medical Monitor or SMC to resume or suspend further injections (either for an individual child or an entire dose Group) will be communicated in writing to the sponsor and Principal Investigator. All communications from the SMC will subsequently be forwarded by the investigators to the IRB.

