6.3 Follow-up

Study Day 1

1. Perform basic history and physical exam (including injection site), emphasizing examination of any acute complaints (i.e., AE data collection).
2. Record vital signs.
3. Obtain a urine sample for metabolomics study.

Study Day 3 +/- 1

1. Perform basic history and physical exam (including injection site), emphasizing examination of any acute complaints.
2. Record vital signs.
3. Obtain a urine sample for metabolomics study.

Study Day 7 +/- 1

1. Perform basic history and physical exam (including injection site), emphasizing examination of any acute complaints.
2. Record vital signs.
3. Obtain blood for anti-Na-GST-1 and anti-Na-APR-1 (M74) antibody assays and cellular immunology assays.
4. Obtain a urine sample for metabolomics study.

Study Day 14 +/- 2

1. Perform basic history and physical exam (including injection site), emphasizing examination of any acute complaints.
2. Record vital signs.

3. Obtain blood for hematology, biochemistry, anti-Na-GST-1 and anti-Na-APR-1 (M74) humoral and cellular immunology assays.
4. Obtain a urine sample for metabolomics study.

Study Day 28 +/- 4

1. Perform basic history and physical exam (including injection site), emphasizing examination of any acute complaints.
2. Record vital signs.
3. Obtain blood for anti-Na-GST-1 and anti-Na-APR-1 (M74) humoral and cellular immunology assays.
4. Obtain a urine sample for metabolomics study.

Study Day 56 +/- 7 (Day of Second Vaccination)

1. Perform basic history (including concomitant medications) and physical exam (including injection site), emphasizing examination of any acute complaints.
2. Obtain blood for hematology, biochemistry, anti-Na-GST-1 and anti-Na-APR-1 (M74) humoral and cellular immunology assays.
3. Obtain a urine sample for metabolomics study.
4. Record vital signs.
5. Administer the vaccine.
6. Observe for at least 1 hour after vaccination to evaluate for immediate adverse reactions.

Study Day 57 (1 day after Second Vaccination)

1. Perform basic history and physical exam (including injection site), emphasizing examination of any acute complaints.
2. Record vital signs.

Study Day 59 (3 +/- 1 days after Second Vaccination)

1. Perform basic history and physical exam (including injection site), emphasizing examination of any acute complaints.
2. Record vital signs.
3. Obtain a urine sample for metabolomics study.

Study Day 63 (7 +/- 1 days after Second Vaccination)

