1. Perform basic history and physical exam (including injection site), emphasizing examination of any acute complaints.
2. Record vital signs.
3. Obtain blood for anti-Na-GST-1 and anti-Na-APR-1 (M74) humoral and cellular immunology assays.
4. Obtain a urine sample for metabolomics study.

Study Day 70 (14 +/- 2 days after Second Vaccination)

1. Perform basic history and physical exam (including injection site), emphasizing examination of any acute complaints.
2. Record vital signs.
3. Obtain blood for hematology, biochemistry, anti-Na-GST-1 and anti-Na-APR-1 (M74) humoral and cellular immunology assays.
4. Obtain a urine sample for metabolomics study.

Study Day 84 (28 +/- 4 days after Second Vaccination)

1. Perform basic history and physical exam, emphasizing examination of any complaints.
2. Record vital signs.
3. Obtain blood for anti-Na-GST-1 and anti-Na-APR-1 (M74) humoral and cellular immunology assays.
4. Obtain a urine sample for metabolomics study.

Study Day 112 +/- 14 [Groups 1a, 2a, & 3a] or 180 [Groups 1b, 2b, & 3b]

(Day of Third Vaccination)

1. Perform basic history (including concomitant medications) and physical exam (including injection site), emphasizing examination of any acute complaints.
2. Obtain blood for hematology, biochemistry, anti-Na-GST-1 and anti-Na-APR-1 (M74) humoral and cellular immunology assays.
3. Obtain a urine sample for metabolomics study.
4. Record vital signs.
5. Administer the vaccine.
6. Observe for at least 1 hour after vaccination to evaluate for immediate adverse reactions.

Study Day 113/181 (1 day after Third Vaccination)

1. Perform basic history and physical exam (including injection site), emphasizing examination of any acute complaints.
2. Record vital signs.
3. Obtain a urine sample for metabolomics study.

Study Day 115/183 (3 +/- 1 days after Third Vaccination)

1. Perform basic history and physical exam (including injection site), emphasizing examination of any acute complaints.
2. Record vital signs.
3. Obtain a urine sample for metabolomics study.

Study Day 119/187 (7 +/- 1 days after Third Vaccination)

1. Perform basic history and physical exam (including injection site), emphasizing examination of any acute complaints.
2. Record vital signs.
3. Obtain blood for anti-Na-GST-1 and anti-Na-APR-1 (M74) humoral and cellular immunology assays.
4. Obtain a urine sample for metabolomics study.

Study Day 126/194 (14 +/- 2 days after Third Vaccination)

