8.2 Methods and Timing for Assessing, Recording, and Analyzing Safety Parameters

8.2.1 Adverse Events

An adverse event (AE) includes any noxious, pathological or unintended change in anatomical, physiological or metabolic functions as indicated by physical signs, symptoms and/or laboratory-detected changes occurring in any phase of the clinical study, whether associated with the study vaccine or placebo, and whether or not considered vaccination related. This includes an exacerbation of pre-existing conditions and intercurrent illnesses.

All AEs will be graded for severity and relationship to study vaccine. A study clinician will be readily available for the duration of the trial to assess AEs. Should a parent/guardian or child call on a study clinician to report an AE, it will be fully documented in their study chart, and discussed with the Principal Investigator.

All AEs will be assessed by the investigator using the following protocol-defined grading system, as or described in Tables 2-5:

Grade 1: **Mild** - No effect on activities of daily living; no medical intervention/therapy required

Grade 2: **Moderate** - Partial limitation in activities of daily living (can complete $\geq 50\%$ of baseline); no or minimal medical intervention/therapy required

Grade 3: **Severe** - Activities of daily living limited to $< 50\%$ of baseline; medical evaluation/therapy required

All AEs will have their possible relationship to study vaccine assessed using the following terms:

Definite: Clear-cut temporal association, and no other possible cause.

Probable: Clear-cut temporal association and a potential alternative etiology is not apparent.

Possible: Less clear temporal association; other etiologies also possible.

Unlikely: Temporal association between the AE and the vaccine or the nature of the event is such that the vaccine is not likely to have had any reasonable association with the observed illness/event (cause and effect relationship improbable but not impossible).

Not Related: The AE is completely independent of vaccine administration; and/or evidence exists that the event is definitely related to another etiology.

The degree of certainty with which an AE can be attributed to administration of study vaccine will be determined by how well the event can be understood in terms of one or more of the following:

1. The event being temporally related with vaccination or reproduced on re-vaccination.

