Arthritis	Mild pain with inflammation, erythema or joint swelling – but not interfering with function	Moderate pain with inflammation, erythema or joint swelling – interfering with function, but not with activities of daily living	Severe pain with inflammation, erythema or joint swelling – and interfering with activities of daily living
Vasovagal episode (associated with a procedure of any kind)	Present without loss of consciousness	Present with transient loss of consciousness	Not Applicable
Cough	Transient-treatment no	Persistent cough; treatment responsive	Paroxysmal cough; uncontrolled with treatment
Bronchospasm, Acute	Transient; treatment; 70% - 80% FEV ₁ of peak flow	Requires treatment; normalizes with bronchodilator; FEV ₁ 50% - 70% (of peak flow)	No normalization with bronchodilator; FEV ₁ 25% - 50% of peak flow; or retractions present
Dyspnea	Dyspnea on exertion	Dyspnea with normal activity	Dyspnea at rest
Hypersensitivity	Transient flushing or pruritus without rash	Pruritic rash or mild urticaria	Symptomatic bronchospasm, with or without urticarial

Table 4: Assessment of Basic Body Function Adverse Event Severity

Vital Signs*	Mild (Grade 1)	Moderate (Grade 2)	Severe (Grade 3)
Tachycardia – beats per minute	115-130	131-150	>150
Bradycardia – beats per minute	55-59	50-54	<50
Hypertension** (systolic, mm Hg)	126-135	136-145	>145
Hypertension** (diastolic, mm Hg)	86-90	91-96	>96
Hypotension	Symptomatic, oral fluids not required	Symptomatic, corrected with oral fluid replacement	Symptomatic, IV fluids indicated

*Subject should be at rest for measurement of vital signs

**With repeat testing at same visit

Table 5: Assessment of Laboratory Adverse Event Severity

HEMATOLOGY	Grade 1 (Mild)	Grade 2 (Moderate)	Grade 3 (Severe)
Hemoglobin	8.2 – 9.2 g/dL	7.1 – 8.1 g/dL	<7.0 g/dL
Platelets	110,000 130,000/mm ³	– 90,000 109,999/mm ³	– <90,000/mm ³
WBCs (increase)	13,800 17,000/mm ³	– 17,001 20,000/mm ³	– <20,000/mm ³
WBCs (decrease)	2500 – 4200/mm ³	1500 – 2499/mm ³	<1500/mm ³
ANC (decrease)	750 – 1000/mm ³	500 – 749/mm ³	<500/mm ³
CLINICAL CHEMISTRIES	Grade 1	Grade 2	Grade 3
Serum creatinine	1.2 – 1.4 mg/dL	1.5 – 1.7 mg/dL	>1.8 mg/dL or requires dialysis
ALT	48 – 105 U/L	106 – 220 U/L	>220 U/L

All local (injection-site) reactions occurring within the first 14 days after vaccination will be considered definitely related to vaccination.

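### The severe-reaction criterion for withholding a later dose names only the first vaccination, so some resolved severe reactions to dose 2 are not a named reason to withhold dose 3

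*Combined protocol and SAP*

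**What the plan says.** Section 4.3.4 introduces its list with "The second or third study vaccination may not be administered to a child if any of the following criteria are met". The list therefore applies before dose 2 and before dose 3. Three bullets deal with reactions or abnormalities by severity:

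- Adverse events: "Any unresolved or continuing solicited or unsolicited Grade 3 adverse event". A resolved Grade 3 event does not meet this.
- Laboratory values: a Grade 3 value that has not come down to Grade 2 or less. This bullet refers to both later doses.
- Past severe reactions: "Severe or sustained reaction or disability related to the first study vaccination". This bullet refers to dose 1 only.

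The same list has discretionary or general grounds: a medical condition that the investigator thinks poses a risk, other reasons at the investigator's judgment, loss of eligibility, and new information that makes further vaccination unsafe. Section 4.3.6 provides for a recommendation by the Independent Medical Monitor or the SMC "to resume or suspend further injections (either for an individual child or an entire dose Group"). Section 8.5 suspends vaccination pending review after a single related SAE, AESI or Grade 3 hypersensitivity reaction. For other related Grade 3 clinical events it requires three or more children of one Group with the same event.

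**The concern.** A criterion placed in a list for two doses covers only one of them, and the protocol gives no reason for the difference. The same reaction in the same child is a named ground for withholding the next dose if it follows dose 1, but rests on judgment or on a general clause if it follows dose 2. The discretionary routes exist after dose 1 as well, and the protocol still saw fit to name the criterion there. At stake is the consistency of an individual safety rule for children aged 6 to 10. Sample size, error rates and planned analyses are not affected.

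**Working it through.** **1. Which named rules cover a severe related reaction to dose 2?**

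| Type of reaction to dose 2 | Named rule | Covered? |
|---|---|---|
| Grade 3, not resolved | 4.3.4, adverse-event bullet | Yes |
| Grade 3 laboratory value that stays at Grade 3 | 4.3.4, laboratory bullet | Yes |
| Severe allergic reaction | 4.3.4 eligibility bullets with exclusion 9 in 4.2; 8.5 for Grade 3 hypersensitivity | Yes |
| Related SAE or AESI | 8.5, one case suffices | Yes |
| Same related Grade 3 clinical event in three or more children of a Group | 8.5 | Yes |
| Resolved, non-serious, non-allergic, not an AESI, fewer than three children | None | No |

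The signs-and-symptoms bullet in 4.3.4 provides for deferral until resolution, and section 5.3 adds no criterion of its own. The last row is the gap. Section 8.2.1 labels Grade 3 as severe ("Grade 3: Severe - Activities of daily living limited to" less than half of baseline). If the bullet uses the word in that sense, Table 2 puts a resolved fever above 39.0°C, or injection-site pain that prevented daily activity, in the gap. A narrower sense leaves fewer events, but the restriction to dose 1 remains.

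**2. Would such a reaction usually have resolved by dose 3?** The visit days are "Study Day 56 +/- 7 (Day of Second Vaccination") and "Study Day 112 +/- 14 [Groups 1a, 2a, & 3a] or 180 [Groups 1b, 2b, & 3b"]; Appendix A2 gives ±14 days for Day 180.

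- Nominal interval from dose 2 to dose 3: 112 − 56 = 56 days, or 180 − 56 = 124 days.
- Shortest interval within the windows: (112 − 14) − (56 + 7) = 35 days, or (180 − 14) − (56 + 7) = 103 days.
- Time left after the 14-day solicited period: 35 − 14 = 21 days, or 103 − 14 = 89 days.

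These are in-window figures, not absolute minimums, because 4.3.4 and 5.3 allow dosing outside the window with Sponsor approval. It is plausible, though not documented, that a transient reaction would be over by then, so that the bullet on unresolved events would not apply.

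**3. How many children?** The halting rule sets a ceiling. For one type of related Grade 3 clinical event, at most 2 of 20 children per Group, or 2 × 3 = 6 of 60, can be affected without reaching it. Events after any dose count toward the three.

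The only related figure in the documents is the adult trial at the same site (section 1.1, co-administration experience): 32 adults, three sets of injections each, and one possibly related Grade 3 event, a high fever.

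- 32 × 3 = 96 sets, so 1/96 ≈ 1.0% per set.
- 60 × 1/96 ≈ 0.6 children after dose 2 in this trial.

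This is a rough assumption. The adult data were still blinded and included the comparator, the schedule was 0, 1 and 6 months, both antigens carried GLA-AF, and there was no 10 µg dose. A range is therefore shown, for p = the rate of one such event type after dose 2 and 16 hookworm-vaccine children per Group (48 in all):

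| Assumed p | Expected of 48 (48p) | At least 1 in a Group, 1 − (1 − p)^16 | 3 or more in a Group | 1 or 2 in a Group |
|---|---|---|---|---|
| 1% | 0.5 | 14.9% | 0.05% | 14.8% |
| 3% | 1.4 | 38.6% | 1.1% | 37.4% |
| 5% | 2.4 | 56.0% | 4.3% | 51.7% |
| 10% | 4.8 | 81.5% | 21.1% | 60.4% |

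The last two columns are exact binomial and count dose-2 events only, so they somewhat understate how often the halting rule would be met. At low rates the rule would usually not close the gap for an individual child.

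**4. What would withholding dose 3 cost the secondary endpoint?** There are 8 hookworm-vaccine children per dose and schedule, or 16 with schedules pooled. The half-width of the 95% CI for mean log IgG, in SD units, is t(0.975, n − 1)/√n.

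- n = 8: 0.836; n = 7: 0.925, so +10.6%.
- n = 16: 0.533; n = 15: 0.554, so +3.9%.

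**The case against.** The strongest reply is that nothing obliges anyone to give dose 3, and this stands. Besides investigator judgment (4.3.4 and exclusion 7 in 4.2), the list has the new-information bullet. The SAE definition in 8.2.3 includes important medical events that may jeopardize the child, so a clinically worrying reaction can be classed as serious, and one related SAE suspends vaccination. The Medical Monitor or the SMC can act for one child. Nor would the reaction go unseen: section 7.1 schedules assessments on Days 1, 3, 7, 14 and 28 after each dose, and section 6.3 repeats history and examination on the day of dose 3. A reader might infer that the protocol forces, or fails to prevent, an unsafe third dose. The documents do not support that.

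The lead-in 'may not' could also mean 'might not' rather than 'must not'. On the permissive reading, naming a criterion matters less, but the difference between dose 1 and dose 2 remains.

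A wider bullet could also catch trivial or unrelated events. If severe means Grade 3, a resolved redness above 25 mm would qualify, since "All local (injection-site) reactions occurring within the first 14 days after vaccination will be considered definitely related to vaccination". In a malaria-endemic area, so might a fever judged possibly related. Both points are fair, but they apply equally to the bullet as it now stands for dose 1, where the protocol accepts them.

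**Conclusion.** The point holds as a narrow inconsistency in a safety rule: one class of dose-2 reactions lacks the named criterion that the protocol provides after dose 1. This conclusion rests on the text and on no event rate. That few children are likely to be affected does rest on the adult figure, which gives about 0.6 children and is only a rough guide. A reader might take the ceiling of 6 of 60 as an expected number; it is only the limit set by the halting rule for one event type. Minor, and cheap to improve.

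**What to change.** In the severe-reaction bullet of 4.3.4, replace 'the first' by 'any previous' and leave the rest unchanged. Add no exception for resolved redness or swelling, because it would also loosen the protection that now applies after dose 1.

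The cost is that an occasional child may miss dose 3 and so have no true value for IgG about 14 days after the third vaccination. Under section 5.3 safety visits and blood sampling continue, but they do not replace that value. At the same SD, the loss of precision is about 11% in CI width for 1 of 8 children, or about 4% for 1 of 16. Losses could be more frequent at the higher doses. The protocol already accepts this kind of cost after dose 1.

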4.3.5 Handling of Withdrawals

The primary reason for withdrawal from the study will be recorded on the appropriate data collection form. Parents/guardians will be encouraged to have their child complete the Early Termination Visit. The Early Termination Visit procedures are listed in **Section 7.5**. Although children are free to withdraw at any time or may be withdrawn by the Principal Investigator or appropriate co-investigator at any time, those who receive at least one dose of study vaccines will be encouraged to remain in the study for follow-up safety assessments and collection of venous blood samples for immunogenicity testing. Every attempt will be made to follow all adverse events, including solicited injection site and systemic reactions, serious adverse events, and new-onset chronic medical conditions ongoing at the time of early withdrawal to resolution.

In the case of children who fail to appear for a follow-up safety assessment, extensive efforts (i.e., three documented contact attempts via in-person visits to the child's home, made on separate

occasions) will be made to locate or recall them, or at least to determine their health status. These efforts will be documented in the child's records.

4.3.6 Termination of Study

If a dose of vaccine is considered significantly reactogenic (see Section 8.5) dose escalation and/or additional vaccinations will be suspended until reviewed by the Independent Medical Monitor, SMC, and study sponsor. Any recommendation of the Independent Medical Monitor or SMC to resume or suspend further injections (either for an individual child or an entire dose Group) will be communicated in writing to the sponsor and Principal Investigator. All communications from the SMC will subsequently be forwarded by the investigators to the IRB.

